2.6 SUBJECT PARTICIPATION AND INFORMED CONSENT

Subjects or their legally authorized representative will be informed of the study and invited to participate. Informed consent must be obtained from each subject or legally authorized representative prior to any clinical investigation participation (including the Baseline Phase), using the Informed Consent Form (ICF) HIPAA authorization form or any other applicable permission form(s) required by law approved by the IRB. The subject/legally authorized representative will be provided with a copy of the Informed Consent Form and HIPAA authorization form or any other applicable permission form(s) required by law and its content will be reviewed verbally with the subject/legally authorized representative by the study investigator or authorize delegate, allowing adequate time for review and questions. The study investigator or authorized delegate will fully explain to the subject or legal representative the

nature of the research, clinical investigation procedures, anticipated benefits, and potential risks of participation in the clinical investigation. All information pertinent to the study shall be provided in writing and in native, non-technical language that is understandable to the subject or subject's legally authorized representative.

Once the subject/legally authorized representative has read and understands the Informed Consent Form and HIPAA authorization form or any other applicable permission form(s) required by law, he/she will indicate his/her willingness to participate in the study by signing the form(s).

If a subject or legally authorized representative is unable to read or write, the informed consent shall be obtained through a supervised oral process. An independent witness shall be present throughout the process. Upon completion of the supervised oral process, the Informed Consent Form, HIPAA authorization form or any other applicable permission form(s) required by law must be signed and dated by the subject or legal representative and by the person obtaining the consent attesting that the information was accurately explained and that informed consent was freely given.

The informed consent process will be fully documented by the investigator or authorized delegate in the medical record and include the date on which the consent was obtained. The original signed consent form HIPAA authorization form or any other applicable permission form(s) required by law will be retained in the subject's study records. A copy of the signed informed consent HIPAA authorization form or any other applicable permission form(s) required by law will be provided to the subject or legal representative and a copy placed in the subject's medical record. Following signing of the consent and HIPAA authorization form or any other applicable permission form required by law the subject's eligibility for the study will be determined.

If new information becomes available during the study that can significantly affect a subject's future health and medical care, or willingness to continue in the study, that information will be provided to the subject(s) in writing.

2.7 ENROLLMENT

Subjects will be considered enrolled in the study after informed consent and HIPAA authorization form or any other applicable permission form required by law has been signed and the subject has been randomized. The following terms will be used to describe potential study participants who do not fully implement the assigned therapy:

- **Non-Consented Screen Failure** - Subject who are screened to participate in the study but do not sign the Informed Consent Form and HIPAA authorization form or any other applicable permission form required by law. These subjects will not be considered enrolled in the study.
- **Consented Screen Failure** - Subject/legally authorized representative who signs the Informed Consent Form and HIPAA authorization form or any other applicable permission

form required by law, but the subject does not meet eligibility criteria. These subjects will not be considered enrolled in the study.

- **Intent-to-Treat** - A subject will be considered part of the intent-to-treat analysis population as long as she/he is randomized into the study, with no adjustment made for whether the device was implanted, compliance with treatment, or events occurring after randomization. These subjects will be enrolled in the study and included in the primary endpoint analysis.

2.8 SUBJECT WITHDRAWAL/DISCONTINUATION CRITERIA

A subject may be considered discontinued from the study if (including but not limited to):

- Subject/legally authorized representative withdraws consent;
- Subject is lost to follow-up;*
- Subject dies;
- Subject completes the study-required follow-up;
- Study management decision by Sponsor to end the study as a whole or just at a particular study location;
- Subject discontinued due to medical necessity by investigator or upon request of a regulatory body; or
- Study site prematurely terminates its participation in the study;

**The following actions will be undertaken prior to categorizing a subject as lost to follow-up. Two attempts will be made to contact the subject via phone, email, or mail. If no response is obtained, a registered or certified letter will be sent to the subject as a last means of contact.*

2.9 BASELINE EVALUATION

Informed consent will be obtained from the subject/legally authorized representative prior to conducting any study related activities.

The following baseline testing will be performed:

1. Medical History
2. Physical exam (PE)
3. National Institute of Health (NIH) Stroke Scale - All personnel conducting any study required NIHSS evaluations are required to have received training and certification per nationally accepted guidelines such as American Stroke Association, or American Academy of Neurology, or National Institute of Neurological Disorders and Stroke
4. Modified Rankin
5. Magnetic Resonance Imaging (MRI) of the head/brain must include FLAIR, DWI, ADC maps, and gradient echo (GRE) among other sequences.

Note: If medically contraindicated to MRI, subjects should have a Computed Tomography (CT) of the head performed

6. CHADS₂ assessment
7. Pregnancy test (required only for females of child bearing potential)
8. 12 Lead ECG
9. Transesophageal echocardiography (TEE) - If thrombus is detected, subject may be rescreened by TEE, after 12 weeks of anticoagulation therapy for consideration of device placement following documentation of absence of intracardiac thrombus
10. INR assessment (only for subjects who are warfarin therapy) – Subjects on warfarin whose INR is not in the target range (at baseline) may return for rescreening once target INR is achieved. During rescreening, subjects must demonstrate two consecutive INRs within the target range (2-3).
11. Medication Determination and Assessment

OMT and concomitant use of aspirin therapy prior to randomization:

The principal investigator should determine appropriate OMT and need for concomitant aspirin therapy as medically indicated for each subject. Subjects must remain on the assigned OMT (warfarin or dabigatran with or without concomitant aspirin therapy) for one month prior to enrollment (defined as time of informed consent, HIPPA and randomization). Should the subject's medical condition change, the Principal Investigator may make changes in the OMT and / or aspirin therapy regimen as needed; however, the subject must take the newly assigned OMT for a minimum of one month prior to randomization. Re-screening rules pertaining to both inclusion and exclusion criteria will apply. All medication changes and accompanying rationale must be documented on the medication log.

12. Hematology Parameters
 - a. Hemoglobin
 - b. Hematocrit
 - c. Serum Creatinine
 - d. Platelets
13. Coagulation parameters
 - a. Fibrinogen antigen
 - b. Quantitative D-dimer
 - c. Von-Willebrand antigen
 - d. Thrombin-Antithrombin complex
 - e. Prothrombin fragment 1.2
 - f. Homocysteine
 - g. tPA antigen
 - h. PAI-1 antigen
14. Neurological Symptoms Interview

15. Quality of Life Interview (EQ-5D-3L)

2.10 RANDOMIZATION

After subject has signed informed consent, HIPAA authorization form or any other applicable permission form required by law and meets all inclusion and none of the exclusion criteria, the subject will be randomized.

A medical management decision, treatment with warfarin or dabigatran* will be made by the principal investigator prior to randomization. The principal investigator must document the optimal medical therapy including the concomitant use of aspirin prior to randomization on the baseline case report form. Subjects will be randomized to either the device arm or the control arm respectively in a 2:1 ratio. Randomization will be stratified by study center, oral anticoagulant therapy (warfarin or dabigatran), and baseline concomitant aspirin usage. Randomization into the concomitant aspirin strata will be capped at 20% of total study enrollment.

**Dabigatran dosing (75 mg or 150 mg bid) should be in accordance with its approved directions for use.*

Subjects in both groups will be assigned a subject ID number at the time of consent. Subjects who are randomized to the device arm must follow the pre-procedure care instructions (Section 2.11.1). The implant procedure must be performed within fourteen (14) days of randomization.

Subjects who are randomized to the control arm must continue taking the OMT that has been assigned by the principal investigator until a primary endpoint is met or the study is completed. Those subjects on warfarin should maintain an INR between 2-3 with adjustment of dosage as needed. Discontinuation of designated OAC (warfarin, dabigatran) or addition of other anticoagulants or antiplatelet medications is not allowed unless medically necessary.

2.11 AMPLATZER CARDIAC PLUG IMPLANTATION PROCEDURE

2.11.1 PRE PROCEDURE CARE

a. Bridge regimen for subjects on warfarin

- Stop warfarin 4 days prior to the day of procedure
- Start Lovenox 2 days prior to the day of procedure at 1 mg/kg subcutaneously every 12 hours for 2 days (subjects with renal dysfunction may require dosage adjustment as determined by the physician)
- On day of the procedure do not administer Lovenox or warfarin

Example: Day 5 is day of procedure:

- Day 1 – stop warfarin
- Day 2 – no medications (Lovenox or warfarin)
- Day 3 – begin Lovenox at 1 mg/ kg subcutaneously every 12 hours

- Day 4 – continue Lovenox at same dosage
- Day 5 - procedure day, no Lovenox (or warfarin)

INR Test

INR must be tested within 24 hours prior to the procedure. An INR should be ≤ 1.5 in order to proceed with the device implantation procedure.

[figure not shown]
b. Bridge regimen for subjects on dabigatran

Discontinue dabigatran 1 to 2 days ($\text{CrCl} \geq 50$ mL/min) or 3 to 5 days ($\text{CrCl} < 50$ mL/min) before invasive or surgical procedures (see dabigatran prescribing information by manufacturer).

2.11.2 PROCEDURE (RANDOMIZED TO DEVICE ARM)

- Procedure must be performed within 14 days from the date of randomization.
- Procedure will be performed under TEE and angiographic guidance.
- On an angiogram assessment, if a subject has an LAA landing zone measured with a width of less than 12.6mm (at its widest point) or greater than 28.5mm at its widest point, the subject will not proceed with device implantation. These subjects will be considered intent to treat.
- On an angiogram assessment, if a subject has insufficient space (minimum 10 mm) distal to the LAA orifice to accommodate insertion of the dilator and sheath, the subject will not proceed with device placement. These subjects will be considered as intent to treat.
- Refer to the Instructions for Use for the recommended device size, delivery sheath selection, and ACP implantation procedure.

2.11.3 ENROLLMENT SCHEME

2.11.4 POST PROCEDURE CARE THROUGH HOSPITAL DISCHARGE

2.11.4.1 Post procedure care for the device arm (for subjects who are randomized to the device arm and receive the device) is to be as follows:

- Subjects must be kept overnight (24 hour stay) for observation.
- Subjects must return to OMT (assigned by the principal investigator at time of randomization) as described below.

2.11.4.1.1 Device Subjects Assigned to Warfarin

- Subjects will be discharged from the hospital on warfarin (adjustment of dosage to keep an INR between 2-3 must be made during the study while subjects are on warfarin). Until the subject's INR is between 2 and 3, Lovenox 1mg/kg subcutaneously twice a day should be administered starting within 24 hours after the procedure.
- INR testing should commence 2-3 days after the initiation of warfarin therapy and be tested frequently until a stable dose/INR has been achieved and then at least every 4 weeks subsequently.

2.11.4.1.2 Device Subjects Assigned to Dabigatran

- Dabigatran therapy* should be re-started after wound hemostasis is satisfactory in accordance with its approved directions for use). Subjects will be discharged from the hospital on dabigatran. Dabigatran dosing* should be in accordance with its approved directions for use.

**Dabigatran dosing (75 mg or 150 mg bid) should be in accordance with its approved directions for use.*

2.11.4.2 Post procedure care for subjects who are randomized to the device arm but do not receive a device (or device is removed) is required as follows:

2.11.4.2.1 Device Subjects Assigned Warfarin

- Subjects are discharged from the hospital on warfarin and will continue to take warfarin throughout the duration of the clinical trial (adjustment of dosage to keep an INR between 2-3 must be made during the study while subjects are on warfarin), or until a primary endpoint is met or the study is completed.
- For attempt to treat subjects who stopped warfarin, until the subject's INR is between 2 and 3, Lovenox 1mg/kg sq, twice a day, should be administered starting the day after the procedure.
- INR testing should commence 2-3 days after the initiation of warfarin therapy and be tested frequently until a stable dose/INR has been achieved and then at least every 4 weeks subsequently.

- Discontinuation of warfarin or addition of other anticoagulants or antiplatelet medications is not allowed unless medically necessary.

[figure not shown]
2.11.4.2.2 Device Subjects Assigned to Dabigatran

- Subjects will be discharged from the hospital on dabigatran and will continue to take dabigatran throughout the duration of the clinical trial or until a primary endpoint is met or the study is completed.
- Discontinuation of dabigatran or addition of other anticoagulants or antiplatelet medications is not allowed unless medically necessary.

2.12 FOLLOW-UP REQUIREMENTS (REFER TO APPENDIX D)

1. Refer to section 2.12.1, 2.12.2, and 2.12.3.
2. Adverse events for all randomized subjects will be collected from the time of informed consent through discontinuation or end of the study.
3. For subjects randomized to control arm and those subjects who are randomized to device arm but do not undergo an implant attempt, follow-up windows are calculated based on the day of randomization. For subjects who undergo an implant attempt and/or receive the device, follow-up windows are calculated from the date of procedure. Subjects who are on warfarin should maintain an INR between 2-3 INR levels must be documented on an INR log. (REFER TO APPENDIX D)
4. Post procedure TEE requirements for the device arm subsequent to hospital discharge: Refer to TEE flow chart below.
5. For subjects randomized to the device arm, once OAC therapy is discontinued, aspirin (325 mg daily) must be started and continued throughout the duration of the trial. If the subject is already on aspirin 81 mg daily, increase dosage to 325 mg daily.
6. Bacterial endocarditis prophylaxis should be carried out for at least six months post procedure (see Appendix C).
7. For subjects who receive the device, a telephone call must be scheduled 3 months (+/- 10 days) post discontinuation of OAC therapy to inquire if subjects have restarted OAC therapy. Telephone call will be documented as an Interim Visit.
8. If during a phone follow-up, a serious adverse event is reported or a response of “Yes” or “Don’t know” to any question on Neurological Symptom Interview is elicited, an in-person interim office visit is required.
9. If asymptomatic cerebral hemorrhage is detected through imaging, please note that there are no standardized clinical guidelines or treatment recommendation for the use of antithrombotic therapy based on MR Imaging findings. These subjects in both groups (device and medical management) should be managed per institutional or investigator standard of care.
10. As part of the health economic and quality of life sub-study, hospital bills of enrolled subjects will be collected up to 2 years or until the study is completed. (REFER TO APPENDIX D)

Transesophageal Echocardiogram (TEE) Imaging Schedule
Flow Diagram for Subjects who are randomized to the device arm

2.12.1 ASSESSMENT AND FOLLOW-UP SCHEDULE; SUBJECTS WHO RECEIVE THE DEVICE (REFER TO APPENDIX D)

	Procedure	Pre-discharge (+ 1 day)	45 days (+/-5 days)	3 Month (+/- 10 days) Post OAC Discontinuation Phone Visit ⁸	6 months (+/- 30 days)	12 months (+/-30 days)	18 months (+/-60 days)	2 years (+/- 60 days)	Annually thereafter (+/- 60 days) phone visit ⁴
Physical Exam		X	X		X	X	X	X	
Neurological Symptoms Interview			X		X	X	X	X	X ⁵
Urine Pregnancy Test	X ¹								
12 lead Electrocardiogram		X	X		X	X	X	X	
2-D Color Flow Doppler Transthoracic Echo (TTE)		X				X ⁶		X ⁶	
Transesophageal Echocardiogram (TEE)	X		X		X	X ⁶		X ⁶	
MRI of head/brain ⁷						X		X	
Adverse Event Assessment	X	X	X	X	X	X	X	X	X
Medication Assessment ²	X	X	X	X	X	X	X	X	X
INR Assessment ³									
Quality of Life Assessment(s)						X		X	

¹Urine pregnancy test must be done within 24 hours prior to the procedure (for female subjects of childbearing potential)

²Review and record all and any changes to antiarrhythmic and antiplatelet medications

³INR must be tested within 24 hours prior to the procedure (for those subjects on warfarin). Post procedure- INR testing should commence 2-3 days after the initiation of warfarin therapy and be tested frequently until a stable dose / INR has been achieved and then at least every 4 weeks subsequently. Subjects are recommended to maintain a target INR between 2-3 while they are on warfarin

⁴Follow-up visits after 2 years will be via telephone

⁵If during a telephone visit, an SAE is reported or a response of **Yes or Don't know** to any question on the Neurological Symptoms Interview is elicited an in-person interim office visit is required

⁶Refer to flowchart above

⁷MRI must include FLAIR, DWI, ADC maps, and GRE among other sequences. If subject is medically contraindicated to MRI, a CT of the head must be performed. If asymptomatic cerebral hemorrhage is detected through imaging, please note that there are no standardized clinical guidelines or treatment recommendation for the use of antithrombotic therapy based on MR Imaging findings. These subjects in both groups (device and medical management) should be managed per institutional or investigator standard of care.

⁸ This phone visit must be performed 3 months after a subject stops taking OAC (Note: OAC must be discontinued once no flow or ≤3mm jet into the LAA (via TEE) has been demonstrated

One week equals 7 days. One month = 30 days. One year= 365 days

2.12.2 ASSESSMENT AND FOLLOW-UP SCHEDULE: CONTROL SUBJECTS AND SUBJECTS RANDOMIZED TO THE DEVICE AND DO NOT RECEIVE THE DEVICE

	Procedure ²	Pre-discharge ² (+ 1 day)	45 days (+/-5 days)	6 months (+/- 30 days)	12 months (+/-30 days)	18 months (+/-60 days)	2 years (+/- 60 days)	Annually thereafter (+/- 60 days phone visit) ⁵
Physical Exam		X	X	X	X	X	X	
Neurological Symptoms Interview			X	X	X	X ⁶	X	X ⁶
Urine Pregnancy Test	X ¹							
12 lead Electrocardiogram		X	X	X	X	X	X	
Transthoracic Echocardiogram (TTE) ²		X						
Transesophageal Echocardiogram (TEE) ²	X							
MRI of head/brain ⁷					X		X	
Adverse Event Assessment	X	X	X	X	X	X	X	X
Medication Assessment ³	X	X	X	X	X	X	X	X
INR Assessment ⁴								
Quality of Life Assessment(s)					X		X	

¹For device attempt female subjects of childbearing potential. Must be performed within 24 hours prior to the procedure

²For device attempt subjects

³Review and record all changes to antiarrhythmic and antiplatelet medications

⁴INR must be tested with 24 hours prior to the procedure for device attempt subjects only (for those subjects on warfarin). INR testing should commence 2-3 days after the initiation of warfarin therapy and be tested frequently until a stable dose/INR has been achieved and then at least every 4 weeks subsequently. Subjects are recommended to maintain a target INR between 2-3 while they are on warfarin

⁵Follow-up visits after 2 years will be via telephone

⁶If during a telephone visit, an SAE is reported or a response of **Yes or Don't know** to any question on the Neurological Symptoms Interview is elicited an in-person interim office visit is required

⁷MRI must include FLAIR, DWI, ADC maps, and GRE among other sequences. If subject is medically contraindicated to MRI, a CT of the head must be performed. If asymptomatic cerebral hemorrhage is detected through imaging, please note that there are no standardized clinical guidelines or treatment recommendation for the use of antithrombotic therapy based on MR Imaging findings. These subjects in both groups (device and medical management) should be managed per institutional or investigator standard of care.

One week equals 7 days. One month = 30 days. One year = 365 days

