1.4.3 Secondary Endpoints

Secondary Endpoints to be assessed are:

1. In-hospital procedure success - defined as successful implantation of the ACP device with no reported in-hospital serious adverse events in subjects randomized to the treatment arm
2. "Day 45" clinical success - defined as in-hospital procedure success, closure of LAA documented at Day 45 TEE, no ischemic stroke or peripheral thromboembolism, and discontinuation of warfarin or dabigatran
3. Long-term clinical success - defined as in-hospital procedure success, closure of LAA documented at Day 45 TEE, no ischemic stroke or peripheral thromboembolism, and sustained discontinuation of dabigatran or warfarin (without temporary re-administration) at last available follow-up. 'Sustained discontinuation' is defined as the subject's ability to remain off of dabigatran or warfarin for a minimum of 6 months following discontinuation except in subjects with less than 6 months of follow-up (see below).

'Sustained discontinuation' for those subjects who have less than 6 months of follow-up is defined as the subject's ability to remain off of dabigatran or warfarin for a minimum of 3 months following discontinuation.

4. Device or procedure-related adverse events to include:
 - Device embolization
 - Myocardial perforation (hemopericardium) or any pericardial effusion requiring drainage
 - Endocarditis
 - Thrombus on device
5. Asymptomatic intracerebral or intraventricular hemorrhage
6. Atrial Fibrillation status - specifically defined as those subjects who progress from paroxysmal to persistent AF, or those subjects who progress from persistent to permanent AF
7. Technical success – defined as delivery and release of the ACP device, including recapture and/or replacement, as necessary. This success rate will be calculated among subjects in whom the delivery system enters the body.
8. Transient Ischemic Attack - defined as acute focal neurological deficit (such as focal motor deficit, aphasia, difficulty walking, hemisensory deficit, amaurosis fugax,

blindness, or focal visual deficit) presumed due to focal ischemia, with symptoms persisting greater than or equal to 5 minutes and less than 24 hours, and that is not associated with MR or CT findings of a new cerebral infarct.

9. Complete closure – defined as the absence of flow into the LAA at six (6) months as assessed by TEE.

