- **Atrial fibrillation status** - The rate of atrial fibrillation status, defined as subjects who progress from paroxysmal to persistent AF, or subjects who progress from persistent to permanent AF, will be summarized for differences between the device and control arms. The rates for each group will be summarized, and the difference between the two expressed as an estimate with a corresponding two sided 95% confidence interval. This endpoint will not be considered for labeling purposes.

While the above endpoints will compare the two treatment arms, the following endpoints will only be assessed in the device arm. They will be summarized as estimated rates with corresponding two sided 95% confidence intervals. No formal hypotheses will be performed for these tests.

- **Device or Procedure Related Adverse Events** - The rate of the following device or procedure related adverse event components will be summarized. However confidence intervals will only be summarized for the composite rate, that is, for the percentage of subjects who experience any one of these events.
 - Device embolization
 - Myocardial perforation (hemopericardium) or any pericardial effusion requiring drainage
 - Endocarditis
 - Thrombus on device
- **In-hospital procedure success:** Successful implantation of the ACP with no in-hospital serious adverse events in subjects randomized to the treatment arm
- **“Day 45” clinical success:** In-hospital procedure success, closure of LAA documented at Day 45 TEE, no ischemic stroke or peripheral thromboembolism, and discontinuation of warfarin or dabigatran
- **Long-term clinical success:** In-hospital procedure success, closure of LAA documented at Day 45 TEE, no ischemic stroke or peripheral thromboembolism, and sustained discontinuation of warfarin or dabigatran (without temporary re-administration of warfarin or dabigatran) at last available follow-up. Subjects who continue or restart warfarin or dabigatran due to medical necessity (e.g. for DVT treatment) rather than LAA closure status will not be considered device failures for the purpose of this analysis.
- **Technical Success and Complete Closure** - The secondary endpoints of technical success, and complete closure will only be evaluated in the device arm and will each be summarized as a point estimate with a corresponding

99.5% confidence interval. However, no formal hypotheses will be tested for these endpoints.

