3.3 MINIMIZING THE RISKS

To minimize potential clinical risks to subjects participating in this clinical trial:

- This study will undergo a review and approval process to be monitored by investigational site Institutional Review Boards (IRBs). The IRBs will also review all study-related documents such as the protocol, participant recruitment announcements, and consent forms.
- The FDA will also review the protocol and consent forms.
- Investigators will be carefully selected based on their knowledge of, and experience treating AF.
- Investigators will be trained with regards to implantation technique of the ACP.
- Investigators will be provided with detailed Instructions For Use as a reference.
- The DSMB and/or CEC will have oversight throughout the clinical trial.

- The Steering Committee will act as an advisory board for the pivotal phase.
- Investigators will be required to follow The American Heart Association recommendations for endocarditis prophylaxis during the clinical trial; and
- Investigators or designated personnel administering the NIH Stroke Scale questionnaire will be certified.

In addition, to reduce the risks of specific device related adverse events:

- The subject eligibility criteria include minimum and maximum LAA dimensions to be treated with the ACP, which should minimize the risk of device embolization, device migration and perforation; and
- Subjects will be administered Heparin during the procedure and OMT therapy after the procedure; once warfarin/dabigatran therapy is discontinued, 325mg of aspirin will begin.

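### Section 2.12 #5 keeps device-arm subjects on aspirin 325 mg daily once OAC has stopped and gives no exception if OAC is restarted

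*Combined protocol and SAP*

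**What the plan says.** Section 2.12 #5 is addressed to the whole randomized device arm and reads: "once OAC therapy is discontinued, aspirin (325 mg daily) must be started and continued throughout the duration of the trial". The same item raises a subject already on 81 mg to 325 mg. Section 3.3 repeats the start of the regimen ("once warfarin/dabigatran therapy is discontinued, 325mg of aspirin will begin") and gives no end.

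Three places foresee a return to OAC:

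- 2.12 #7 requires a telephone call three months after OAC is stopped, "to inquire if subjects have restarted OAC therapy".
- The long-term clinical success endpoint in 1.4.3 requires "sustained discontinuation of dabigatran or warfarin (without temporary re-administration) at last available follow-up".
- Section 2.15.4 says how to count subjects who restart for medical reasons, with treatment of deep vein thrombosis as the example.

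Other groups have a different rule. In the control-arm paragraph of 2.10, "addition of other anticoagulants or antiplatelet medications is not allowed unless medically necessary". Sections 2.11.4.2.1 and 2.11.4.2.2 say the same of device-arm subjects who did not receive a device or had it removed, for example "Discontinuation of warfarin or addition of other anticoagulants or antiplatelet medications is not allowed unless medically necessary". Section 2.11.4.1, on implanted subjects, has no such sentence.

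Appendix D closes enrollment at 97 subjects. It exits controls and subjects with a failed implant attempt, and follows implanted subjects to 5 years. Within 2.12 it changes the text of #3 and #10 and leaves #5 alone.

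**The concern.** Item #5 is mandatory, runs to the end of the trial and carries no condition. The event that makes it hazardous, a return to full anticoagulation, is one the protocol asks sites to look for. A site that learns on the three-month call that OAC has been restarted finds no instruction about the aspirin except the standing order to continue 325 mg.

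What is at stake is subject safety in the remaining follow-up. A subject managed exactly as written takes an anticoagulant with 325 mg of aspirin. A clinician who stops or lowers the aspirin departs from the plan, and 2.20.1 counts any such departure as a deviation.

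**Working it through.** No sample size, power or error rate is involved, and the plan gives no figure to reproduce. The check sets the texts side by side, followed by some simple arithmetic on size.

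**1. Does #5 end when OAC resumes?** The trigger is OAC discontinuation and the stated end is the end of the trial. Section 3.3 gives only the trigger. Nothing else in the readable text stops or reduces the aspirin. The footnote to the follow-up schedule on antiplatelet changes asks sites to record them; it does not authorize them.

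**2. Is a restart realistic under the plan?** Yes. 2.12 #7, 1.4.3 and 2.15.4 all provide for it, and none adds an aspirin instruction.

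**3. How does the protocol treat the combination elsewhere?**

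- Exclusion 38 bars aspirin above 81 mg/day at enrollment. Inclusion 3 means that every subject is then on warfarin or dabigatran.
- Section 3.2.3 warns of more bleeding with OAC plus aspirin. It cites a major-bleeding hazard ratio of 1.76 (95% CI 1.55 to 2.00) for aspirin or clopidogrel added to the study anticoagulant in the dabigatran pivotal trial. That figure is not specific to aspirin or to 325 mg.
- Three of the six rows in the 3.2.3 guideline table give an aspirin dose in mg with warfarin: 75–81 mg in two rows (one also with clopidogrel) and below 162 mg in one. These rows concern other indications, and no row gives a dose with dabigatran.
- Dose ratios: 325/81 = 4.0 and 325/162 = 2.0.

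**4. Do 2.10 and 2.11.4.2 bind the same subjects as #5?** For implanted subjects, no. 2.10 speaks of controls, and 2.11.4.2 of device-arm subjects without a device. The only overlap is a device-arm subject without a device who stops OAC and later restarts it, because #5 is worded for everyone randomized to the device arm. Appendix D exits those whose implant attempt failed, so little of that overlap remains.

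**5. Is #5 still in force?** Yes. Appendix D continues device subjects under the protocol with listed changes, and #5 is not listed.

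**6. How many subjects?** The actual split is not given. Expected at 2:1: 97 × 2/3 = 64.7, about 65. Subjects who never received a device, have exited or never stopped OAC come off that number. The documents give no restart rate. If 5% to 20% restarted (an assumption), the result would be 64.7 × 0.05 = 3.2 to 64.7 × 0.20 = 12.9, or about 3 to 13 subjects before those reductions.

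**The case against.** The strongest reply is that 325 mg is plainly a replacement for OAC. Both #5 and 3.3 tie it to stopping OAC, and a sensible investigator would drop or reduce it on restart. That is a reasonable reading of the intent, and many sites may follow it. It does not change the words: the item says what starts the aspirin and when it ends, and a restart is not the end point.

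A second reply is that 3.2.3 leaves OAC with aspirin to the treating physician and repeats the caution for dabigatran. This softens the gap. But the passage belongs to 3.2, the risk assessment of the control arm, and does not mention #5 or lift its requirement.

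Third, the device-arm flow diagram is not shown in the text reviewed, and it may hold an instruction. That cannot be excluded. The diagram is titled as a TEE imaging schedule, however, and an aspirin exception there would still disagree with the plain wording of #5.

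Fourth, aspirin may be wanted for the device itself, since device thrombus is a listed product risk in 3.1.2. This stands. It argues against a fixed instruction to stop aspirin and for leaving the choice to the investigator.

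Fifth, exclusions 1, 28 and 39 remove some reasons for later OAC, enrollment is closed, and the analyses are descriptive. All true, and these facts keep the point small.

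**Conclusion.** The gap is real. As written, an implanted subject who restarts OAC must stay on aspirin 325 mg daily, and doing otherwise is a deviation. This is a small safety point for implanted subjects still in follow-up. It rests on the readable text and on the flow diagram not already settling the matter. No analysis result changes: under Appendix D the primary endpoints are only summarized descriptively, and the secondary endpoints and other analyses are dropped.

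Four stronger readings are tempting, and the documents do not support them:

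- *The protocol contradicts itself.* A reader might infer this from 2.10 and 2.11.4.2. Those rules cover other subjects, who are meant to stay on OAC. They show a stricter approach to the same combination and are not a competing rule for implanted subjects.
- *At most 65 subjects are exposed.* About 65 is the expected device-arm allocation, not a ceiling. The number implanted, off OAC and still in follow-up is not given.
- *81 mg is the protocol's dose limit with OAC.* It is an entry criterion. The protocol sets no aspirin cap for follow-up.
- *The excess bleeding can be estimated.* The documents give neither a restart rate nor a bleeding rate for 325 mg with OAC, and the ratio of 1.76 pools aspirin and clopidogrel.

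**What to change.** Add to 2.12 #5: *If OAC is restarted, the 325 mg aspirin requirement is suspended while the subject is on OAC; aspirin is then stopped or continued at low dose at the investigator's judgment (for example if device thrombus is present), and 325 mg is resumed when OAC is stopped again; these changes are not protocol deviations.*

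This names no numerical cap, keeps discretion with the treating physician, and removes the deviation for a sensible change. If the flow diagram already gives the instruction, #5 should be aligned with it.

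The cost is a short amendment or a letter to the 17 centers, possibly with FDA and IRB approval under 2.20.2 because subject risk is affected. No visit, test or analysis is added.
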